Although we appreciate that inflammation is a driver of acute coronary syndromes (ACS) and strokes, profiling circulating inflammatory mediators (e.g. CRP, cytokines, lipoproteins) has not greatly added to traditional management strategies. One possible explanation for this gap is that circulating inflammatory markers capture the systemic inflammatory state of the patient and not local inflammation in specific arterial beds. In animal models, the innate immune system responds to local plaque rupture, leading to the recruitment of circulating monocytes. In human observational studies, elevated levels of monocytes correlate with infarct and stroke size.⁸ Although it is clear that circulating monocytes are elevated in patients with atherosclerotic diseases, their molecular profiles and how they relate to clinical atherosclerotic cardiovascular disease remain largely unknown. Furthermore, even though it is known that circulating monocytes can change with acute and chronic inflammatory stresses, it remains unclear how PCSK9 inhibition and subacute reductions in lipoproteins impact circulating monocyte subsets and their functional responses. As sentinels of innate immune system, the circulating monocytes may provide a snapshot into local plaque microenvironment providing a functional “biocellular-marker” that integrates both the systemic and local inflammatory state of patients with atherosclerotic disease.⁹

Although experimental models have linked lipoproteins and EC dysfunction with systemic inflammation, relatively little is known about this network in clinical populations and specifically how it changes with PCSK9 inhibition. Because of PCSK9 effects on the LDL receptor, PCSK9 inhibition is likely to inhibit pro-inflammatory changes in circulating monocyte subsets and functions. In circulating monocytes, toll-like receptors (TLR) sense inflammatory molecules. TLR responses are mediated through MyD88 and TRIF, which leads to activation of signaling pathways including ***Jak-STAT, Akt, AMPK, mTOR, PKA, NFKB, and MAPK***, which mediate inflammatory transcriptional programs. The participation of PCSK9 in vascular inflammation is supported by preclinical studies using PCSK9 siRNA in macrophages. These studies have demonstrated that PCSK9 inhibition in macrophages reduces NF- κ B inflammatory responses.¹⁰

Furthermore, oscillatory shear stress increases the activation of pro-inflammatory signaling pathways and reduces activation of anti-inflammatory pathways. As an exploratory aim, we will measure low shear blood viscosity to examine the associations between baseline and on-trial change in low shear blood viscosity with inflammatory mediators. The data on blood viscosity will also be used to support our larger aim concerning the putative role of PCSK9 inhibition on cardiac microvascular dysfunction, as blood flow in the microcirculation is highly dependent on changes in blood viscosity.

Our aim is to define how PCSK9 inhibition alters the circulating monocyte populations and to systematically profile the transcriptional and proteomic responses to TLRs and how these responses are modulated by PCSK9 inhibition in the peripheral blood mononuclear cells (PBMC) clinical samples and relate these molecular signatures to clinical and imaging variables. The overall rationale for the work proposed is to understand the molecular mechanisms through which PCSK9 and circulating lipoproteins orchestrate TLR response in circulating monocytes. The outcome measures for this aim include PBMC subset analysis and transcriptional and proteomic analysis of inflammatory signaling pathways in

response to TLR stimulation. After the proposed studies for this aim have been completed, *it is our expectation that we will have defined the molecular pathways through which PCSK9 modulates inflammatory responses in circulating monocytes and how these molecular signatures relate to clinical variables known to be important in CVD risk stratification.*

Microfluidic technology has recently been applied to molecular biology and to clinical diagnostics. Because of its small sample requirements and exquisite spatial control, microfluidics is an exciting complement to existing diagnostic technologies. We recently engineered microfluidic-proteomic device that allows for the rapid profiling of immune cell activation (Figure 1). Studies have suggested that understanding the molecular signatures associated immune cell stress responses can be more informative than static measures of inflammation. Profiling the activation patterns of circulating monocytes from clinical patients has been difficult because of the amount and processing of clinical samples required for traditional molecular assays. This microfluidic profiling device will overcome many of these obstacles, allowing us to profile the molecular activation patterns of circulating blood monocytes in parallel with markers of systemic inflammation, lipoproteins, and other clinical variables with the requisite throughput and fidelity. This technology will allow us to link the biological effects of PCSK9 inhibition with immune cell function, providing mechanistic insight into the relationship between lipoprotein metabolism, microvascular dysfunction, and inflammation, ultimately resulting in novel surrogate markers that could result in identification of “at-risk” populations that would benefit from more aggressive LDL cholesterol reduction.

Monocytes are key innate immune system mediators of inflammatory responses and have been implicated as drivers of CVD. Monocyte subsets can be characterized using flow cytometry for surface expression of Fc γ III receptor CD16 and the lipopolysaccharide receptor CD14. We will profile monocytes in patients using flow cytometry. Briefly, blood will be collected in Cell Preparation Tubes (CPT) with sodium citrate (BD, New Jersey). Cells will be resuspended in FACS buffer and stained with fluorescently labeled antibodies. Monocyte subsets will be defined using CD14 and CD16. The Nomenclature Committee of the International Union of Immunological Societies defines three monocyte subsets by this method: CD14++CD16- (classical), CD14++CD16+ (intermediate), and CD14+CD16++ (non-classical). Flow cytometric analysis will be performed on a BD Accuri C6 flow cytometer and the data analyzed using FlowJo software (Tree Star, Inc). Monocyte subsets will be defined using CD14 and CD16. Because cholesterol metabolism has been associated with monocyte egress from the bone marrow, we anticipate that PCSK9 inhibition will alter monocyte subsets compared with patients not on therapy.

We will systematically define functional relationships between clinical data, cell-surface markers, and molecular activation of signaling pathways using our microfluidic proteomic platform and PCR arrays. Briefly, circulating monocytes will be isolated and processed as described above. To understand how PCSK9 inhibition modulates transcriptional and signaling responses to inflammatory stimuli, monocytes will be stimulated with TLR ligands and RNA and protein will be isolated at 2 time points (30 min and 2 hours). Inflammatory transcriptional programs will be profiled using PCR arrays (SA Biosciences, Maryland). Activation of inflammatory signaling pathways (MAPK, NFkB, Akt, AMPK, mTOR, Jak-STAT, PKA) will be profiled using our novel microfluidic immunoblotting platform. We anticipate that PCSK9 inhibition will significantly alter TLR activation of signaling pathways and inflammatory transcriptional programs in monocytes. The dynamic responses characteristic of circulating monocytes cannot be captured with typical profiling experiments; we anticipate that by using circulating monocytes as a “biocellular” marker of inflammatory risk, tremendous insight will be gained into how PCSK9 modulates inflammatory responses and these dynamic molecular signatures have the potential to identify patients most at risk of CVD disease and those who would benefit from more aggressive LDL cholesterol reduction.

Circulating biomarkers that interface with inflammation and endothelial function will be measured. These include soluble VCAM-1, ICAM-1, LOX-1, MCP-1 and MIP-1 α . Due to the critical role of low wall shear stress

in endothelial dysfunction, inflammation and site-specificity of atherosclerosis, we will measure blood viscosity profiles. Lipoprotein subclasses will be measured by NMR spectroscopy (LabCorp). The choice of NMR is based on a recent study that showed an inverse association between large HDL particle concentration and myocardial perfusion reserve index.¹¹

[figure not shown]

Figure 1| Schematic of the PDMS microfluidic device. This microfluidic device allows high-throughput targeted-proteomic assessment of signaling pathways in individual patient samples.

1.1. Aims:

We therefore propose to evaluate the effects of evolocumab upon biocellular markers potentially altered by PCSK9 inhibition in a population of type 2 diabetes patients with cardiac microvascular dysfunction.

1.1.1. Primary Objective

Determine the ACUTE and SHORT-TERM effects of PCSK9 inhibition with evolocumab on biocellular markers of inflammation, immune mediated thrombosis and rheology. The data from this trial will be used to support a clinical trial to assess the role of PCSK9 inhibition in type 2 diabetes patients with microvascular dysfunction.

1.1.2. Secondary Objective:

- a) To define the association between PCSK 9 concentrations and immune-related phenotype.
- b) To define the association between Lp(a) concentrations, oxidized phospholipids (OxPL), ApoB, biocellular markers of inflammation, tissue factor and immunothrombosis.

2. SUBJECT ELIGIBILITY

This study can only fulfill its objectives if appropriate subjects are enrolled. In addition to the eligibility criteria listed below, all relevant medical and non-medical considerations will be taken into account when deciding whether an individual subject will be suitable to enter this particular study.

2.1. Inclusion Criteria

- a) Subjects \geq 18 years of age at signing of informed consent
- b) A history of clinical ASCVD, which is defined as: acute coronary syndrome, or a history of MI, stable or unstable angina, coronary or other arterial revascularization, stroke, transient ischemic attack (TIA), or peripheral arterial disease presumed to be of atherosclerotic origin.¹²
- c) Clinical diagnosis of type 2 diabetes according to ADA/CDA guidelines
- d) Subject on stable dose of maximally-tolerated statin therapy for \geq 4 weeks prior to screening and LDL-C \geq 70mg/dL. For subjects whose maximally tolerated dose of statin is no type or dose (i.e. determined to be statin intolerant by primary investigator), background lipid-lowering therapy is not required.
- e) Fasting triglycerides \leq 400 mg/dL (4.52 mmol/L) be central laboratory at screening
- f) Willing and able to comply with scheduled visits, treatment plan, laboratory tests and other trial procedures
- g) Abnormal urinary Albumin Creatinine Ratio (ACR) as defined by an ACR >2 .

2.2. Exclusion Criteria

- a) Personal or family history of hereditary muscular disorders
- b) NYHA III or IV heart failure, or last known left ventricular ejection fraction (LVEF) $<$ 30%
- c) Uncontrolled serious cardiac arrhythmia defined as recurrent and highly symptomatic ventricular tachycardia, atrial fibrillation with rapid ventricular response, or supraventricular tachycardia that are not controlled by medications, in the past 6 weeks prior to randomization
- d) Myocardial infarction, unstable angina, percutaneous coronary intervention (PCI) within 6 weeks, coronary artery graft (CABG) or stroke within 3 months prior to randomization
- e) Planned cardiac surgery or revascularization
- f) Moderate to severe renal dysfunction, defined as an estimated glomerular filtration rate (eGFR) $<$ 30 mL/min/1.73m² at screening.
- g) Type 1 diabetes, poorly controlled type 2 diabetes (HbA1c $>$ 10%), newly diagnosed type 2 diabetes (within 6 months of randomization), or laboratory evidence of diabetes during screening (fasting serum glucose \geq 126 mg/dL [7.0 mmol/L] or HbA1c \geq 6.5%) without prior diagnoses of diabetes
- h) Uncontrolled hypertension defined as sitting systolic blood pressure (SBP) $>$ 160 mmHg or diastolic BP (DBP) $>$ 100 mmHg
- i) Subject who has taken a cholesterol ester transfer protein (CETP) inhibitor in the last 12 months prior to LDL-C screening, such as: anacetrapib, dalcetrapib or evacetrapib

- j) Treatment in the last 3 months prior to LDL-C screening with any of the following drugs: immunosuppresives like cyclosporine, systemic steroids (e.g., IV, intramuscular [IM], or PO) (Note: hormone replacement therapy is permitted), vitamin A derivatives and retinol derivatives for the treatment of dermatologic conditions (e.g., Accutane); (Note: vitamin A in a multivitamin preparation is permitted). Topical retinol prescription and non-prescription derivatives or creams are permitted.
- k) Uncontrolled hypothyroidism or hyperthyroidism as defined by thyroid stimulating hormone (TSH) < 1.0 time the lower limit of normal or >1.5 times the ULN, respectively, at screening. Potential subjects with TSH < 1.0 time the lower limit of normal due to thyroid replacement therapy is not considered an exclusion
- l) Active liver disease or hepatic dysfunction, defined as aspartate aminotransferase (AST) or alanine aminotransferase (ALT) > 3 times the ULN as determined by central laboratory analysis at screening
- m) Known active infection or major hematologic, renal, metabolic, gastrointestinal or endocrine dysfunction in the judgment of the investigator
- n) Diagnosis of deep vein thrombosis or pulmonary embolism or major surgical procedures within 3 months prior to randomization
- o) Unreliability as a study participant based on the investigator's (or designee's) knowledge of the subject (e.g. alcohol or other drug abuse)
- p) Currently enrolled in another investigational device or drug study, or less than 30 days since ending another investigational device or drug study(s), or receiving other investigational agent(s)
- q) Female subject who has either (1) not used at least 1 highly effective method of contraception for at least 1 month prior to screening or (2) is not willing to use such a method during treatment and for an additional 15 weeks after the end of treatment, unless the subject is sterilized or postmenopausal;
 - a. Menopause is defined as: 12 months of spontaneous and continuous amenorrhea in a female \geq 55 years old or 12 months of spontaneous and continuous amenorrhea with a follicle-stimulating hormone (FSH) level > 40 IU/L (or according to the definition of "postmenopausal range" for the laboratory involved) in a female < 55 years old unless the subject has undergone bilateral oophorectomy
 - b. Highly effective methods of birth control include: not having intercourse or using birth control methods that work at least 99% of the time when used correctly and include: birth control pills, shots, implants, or patches, intrauterine devices (IUDs), tubal ligation/occlusion, sexual activity with a male partner who has had a vasectomy, condom or occlusive cap (diaphragm or cervical/vault caps) used with spermicide
- r) Subject who is pregnant or breast feeding, or planning to become pregnant during treatment and/or within 15 weeks after the end of treatment
- s) Use of a PCSK9 inhibitor within 10 weeks from screening visit
- t) Subject who has any kind of disorder that, in the opinion of the investigator, may compromise the ability of the subject to give written informed consent and/or to comply with all required study procedures
- u) Malignancy except non-melanoma skin cancers, cervical or breast ductal carcinoma in situ within the last 5 years

- v) Subject who has known sensitivity to any of the products or components to be administered during dosing
- w) Subject who is likely to not be available to complete all protocol-required study visits or procedures, and/or to comply with all required study procedures to the best of the subject and investigator's knowledge
- x) History or evidence of any other clinically significant disorder, condition or disease (with the exception of those outlined above) that, in the opinion of the principal investigator would pose a risk to subject safety or interfere with the study evaluation, procedures or completion
- y) Blood donation 4 weeks prior to screening, or stated intention to donate blood or blood products during the period of the study or within one month following completion of the study
- z) Subjects who have participated in other studies within 30 days prior to screening, or have five times the plasma half-life (if known) of the investigational drug, whichever is longer.
 - aa) BMI >40 kg/m²

3. STUDY DESIGN

3.1. Study Overview

This is a double-blind, randomized, placebo-controlled, parallel group Phase IV study with two treatment arms: evolocumab SC 420 mg/dL QM or matching placebo. The population will include men and women of non-child-bearing potential with documented CAD and type 2 diabetes.

Approximately 100 subjects will be screened in order to keep 40 subjects to complete the study. Subjects will be followed for 12 weeks during the treatment phase, maintaining the double-blind throughout. Assessments of ACUTE and SHORT-TERM effects of PCSK9 inhibition with evolocumab on biocellular markers of endothelial function will be measured at baseline, Week 2, and Week 12. Safety assessments will be undertaken at each study visit. Subjects whose maximally tolerated dose of statin is no type or dose (i.e. determined to be statin intolerant by primary investigator) must be randomized fairly between 2 treatment arms to prevent selection bias.

Subjects should continue on their stable dose of anti-hyperglycaemic therapies during the course of the study. However, it is important that the haemoglobin A1c (HbA1c) does not rise above 10% and that the patient does not develop severe hypoglycaemia or frequent episodes of mild-moderate hypoglycaemia, as defined by the Canadian Diabetes Association 2008 Clinical Practice Guidelines for the Prevention and Management of Diabetes.¹³

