3.2 Randomization Procedure

A randomization list will be produced using a validated system that automates the random assignment of treatment arms to randomization numbers in the specified ratio. At Visit 2, eligible subjects will be given the lowest available randomization number. This number assigns the patient to one of the treatment arms.

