3.4 Blinding

The identity of the treatments will be concealed by the use of matching placebo to the study drug that are identical in packaging, labeling, appearance and schedule of administration.

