5.9 Concomitant Therapy

Medications are not altered for the purpose of this trial, however, any medication changes during the study must be recorded, as must those started before randomization and continued thereafter. During the hospital stay and at following study visits, changes in concomitant therapy must be recorded.

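### Does the instruction to randomize statin-intolerant subjects fairly need a stratum, or a statin term in the ANCOVA?

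*Combined protocol and SAP*

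**What the plan says.** Inclusion criterion 2.1(d) admits two kinds of subject. Most must meet the requirement "Subject on stable dose of maximally-tolerated statin therapy for" at least 4 weeks before screening. Where the investigator judges that no statin is tolerated, "background lipid-lowering therapy is not required". Section 3.1 returns to this second group and says its members "must be randomized fairly between 2 treatment arms to prevent selection bias".

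The working text on allocation is in section 3.2. A validated system "automates the random assignment of treatment arms to randomization numbers in the specified ratio", and "At Visit 2, eligible subjects will be given the lowest available randomization number". Section 3.2 mentions no stratum, block or minimization factor, and the text available gives no number for the ratio. Section 3.4 describes a placebo "identical in packaging, labeling, appearance and schedule of administration".

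Section 7.3 specifies an ITT ANCOVA adjusted for baseline values. It puts the estimated effects ahead of hypothesis tests and names no statin term. Section 5.9 adds that "Medications are not altered for the purpose of this trial". On size, section 3.1 says "Approximately 100 subjects will be screened in order to keep 40 subjects to complete the study", and section 7.1 calls the study a signal-finding trial whose data will help to size a larger one.

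**The concern.** Section 3.1 places an obligation on one named subgroup, and section 3.2 contains no step particular to that subgroup. The subgroup is also a plausible source of noise. Its members may have no background lipid-lowering therapy, in a trial of how a lipid-lowering drug changes inflammatory and rheological markers. If the sentence was meant to secure similar numbers in each arm, a single unstratified list does not do so, and the primary model has no statin term to pick up what is left. The estimates feed the sizing of a later trial, so a chance excess of statin-free subjects in one arm would matter if it moved them appreciably. A person preparing the list might also wonder whether a second stratum was expected.

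**Working it through.** **Step 1: what the sentence asks for.** Its stated aim is to prevent selection bias, that is, the steering of particular subjects to a particular arm. Three features meet that aim: automated random assignment (3.2), use of numbers in order for every eligible subject (3.2), and indistinguishable placebo (3.4). Chance imbalance is a different matter, and the text sets no target for it. Read by its own purpose, the sentence says that statin-intolerant subjects may not be placed by choice. Section 3.2 then carries it out without further rules.

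**Step 2: how large a chance imbalance could be.** From the documents: 40 completers. Assumed, because the documents do not say: 20 per arm, and k statin-intolerant subjects among the 40. The number in one arm is then hypergeometric.

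For k = 4, a difference of 4 means that all four are in one arm: 2 × C(20,4)/C(40,4) = 2 × 4,845/91,390 = 0.106. A difference of 2 has probability 2 × 1,140 × 20/91,390 = 0.499. The mean absolute difference is 4 × 0.106 + 2 × 0.499 = 1.42. The other values follow in the same way:

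| k | P(difference ≥ 4) | Mean absolute difference |
|---|---|---|
| 3 or fewer | 0 | – |
| 4 | 10.6% | 1.42 |
| 5 | 4.7% | 1.78 |
| 6 | 18.2% | 1.73 |
| 7 | 9.1% | 2.01 |
| 8 | 23.5% | 1.95 |
| 9 | 12.7% | 2.20 |
| 10 | 27.3% | 2.13 |

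**Step 3: what that does to the estimate.** Let d be the amount by which statin-free subjects differ in outcome beyond what the baseline marker explains, assumed to be 0.25 to 1.0 SD. Shift = (difference/20) × d.

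- Average case, low end: 1.42/20 × 0.25 = 0.018 SD.
- Average case, high end: 2.20/20 × 1.0 = 0.11 SD.
- Excess of 4: 4/20 × 0.25 = 0.05 SD, up to 4/20 × 1.0 = 0.20 SD.

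The standard error is √(2/20) = 0.316 SD without gain from baseline, or √(0.75 × 2/20) = 0.274 SD with an assumed baseline correlation of 0.5. Every shift above is smaller than either value. Over repeated randomizations the mean shift is zero, and the variation between statin groups is already part of the residual variance behind the confidence interval.

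**Step 4: what a remedy would gain.** Take p = k/40 and unit residual variance before a statin term is added. The statin term multiplies the standard error by √(1 − p(1−p)d²). On an unstratified list, chance correlation between statin status and arm multiplies it again, on average by 1.0135 (k = 4) or 1.0136 (k = 8). Example for k = 4, d = 0.5: √(1 − 0.09 × 0.25) × 1.0135 = 0.9887 × 1.0135 = 1.002. Stratified blocks of 4 nearly remove the second factor; the last column was obtained by simulation.

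| k | d | Covariate only, change in SE | Stratified list plus stratum term, change in SE |
|---|---|---|---|
| 4 | 0.25 | +1.1% | −0.3% |
| 4 | 0.5 | +0.2% | −1.1% |
| 4 | 1.0 | −3.3% | −4.6% |
| 8 | 0.25 | +0.9% | −0.5% |
| 8 | 0.5 | −0.7% | −2.0% |
| 8 | 1.0 | −7.1% | −8.3% |

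The covariate alone pays only above a break-even d of 0.54 (k = 4) or 0.41 (k = 8). If baseline has already reduced the residual variance to 0.75, these fall to 0.54 × √0.75 = 0.47 and 0.41 × √0.75 ≈ 0.35. Stratifying has a small cost: incomplete blocks in both strata could leave 22 against 18, which multiplies the standard error by √((1/22 + 1/18)/(2/20)) = 1.005.

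**The case for a change.** The strongest opposing case is that the authors would not have written a mandatory sentence about one subgroup merely to repeat that randomization is random. On that view they meant balance and used the wrong term for it. Adjustment for the baseline marker is also only a partial answer: it handles a difference in level, but not a different change from baseline in subjects who take no statin. Stratification would be cheap and would hold the difference to 2 among randomized subjects. Allowing for dropout (48 randomized, each lost with probability 1/6, both assumed), a difference of 4 or more among completers has probability 0 to 1.9% with stratification and 5.3 to 18.8% without, for 4 to 10 such subjects randomized.

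Part of this stands. The word is undefined, the ratio is not given in the text available, and baseline adjustment does not replace a statin term. But a redundant sentence is weak evidence of an unstated balance requirement, because the purpose it gives is met by the list as described. The imbalance probabilities count subjects; once converted to a shift in the estimate they fall within its ordinary sampling error. Built as section 3.2 is written, the list is a single one, and a person preparing it has what is needed apart from the ratio, which a list specification would hold.

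**Conclusion.** The concern does not call for a change. Section 3.1 uses a loose word for something that sections 3.2 and 3.4 already provide, and the ANCOVA in section 7.3 gives a valid estimate with or without balance in this subgroup. Leaving out a stratum and a statin term is a fair trade-off in a 40-subject signal-finding trial. The subgroup may be very small, and the gain from stratifying is about 0.3 to 2% of the standard error for d up to 0.5 SD. A covariate alone changes it by about +1% at d = 0.25 and helps clearly only when d is large.

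The sizes rest on assumed values: 20 per arm, k of 4 to 10, d of 0.25 to 1.0 SD, and a baseline correlation of 0 or 0.5. The documents give none of these. A much larger subgroup, together with a d near 1.0, would make stratification more worthwhile, but nothing in the text points to that. The validity of the planned comparison does not depend on these assumptions.

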4 SCHEDULE OF STUDY PROCEDURES

Screening assessments and study procedures outlined in this section and in Table 1 can only be performed after obtaining written informed consent.

All on-study visits and dosing should be scheduled from Day 1 (first IP administration). For example, the Week 2 visit is 2 calendar weeks after the study Day 1 visit, which corresponds to study Week 2. When it is not possible to perform the study visit at the specified time point, the visit should be performed within the visit window specified in Table 1. If a study visit is missed or late, including visits outside the visit window, subsequent visits should resume on the original visit schedule. Missed assessments at prior visits should not be duplicated at subsequent visits. With the exception of screening, all study procedures for a visit should be completed on the same day if possible.

Visit 1: Screening

- Written informed consent
- Demographics
- Medical history
- Vital signs
- 12 lead ECG measurement
- Concomitant therapy
- Dietary instruction; medication compliance reminder
- Physical examination
- Body height, waist circumference
- Body weight
- Seattle Angina Questionnaire 7 (SAQ7)
- Laboratory assessments: TSH, hematology (CBC), blood chemistry (creatinine/eGFR and electrolytes), Liver Function Tests (ALT, AST), creatinine/eGFR, HbA_{1c}, local lipid panel, urine albumin to creatinine ratio (ACR), urine pregnancy test (if female of child bearing potential)

Visit 2 (Randomization) 7-28 days after Screening

- Review for AEs/SAEs/CV events
- Concomitant therapy
- Vital signs
- Dietary instruction; medication compliance reminder
- Randomization
- Seattle Angina Questionnaire 7 (SAQ7)
- Laboratory assessments: fibrinogen, whole blood viscosity analysis, NMR lipoprotein subclass analysis, Apo B, lipoprotein (a), biocellular marker analysis, Oxidized lipid Analysis
- DNA/mRAN test for lipoprotein and inflammatory polymorphisms that may influence the response to therapy (the specimens will be stocked at site and the tests will be performed later).
- SC IP administration, QM (in-clinic) and 30 minute post-injections observation

Visit 3 (Week 2) ±4 days

- Review for AEs/SAEs/CV events
- Concomitant therapy
- Vital signs

- Dietary instruction; medication compliance reminder
- Seattle Angina Questionnaire 7 (SAQ7)

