- Laboratory assessments: hematology (CBC), blood chemistry (creatinine/eGFR, electrolytes), Liver Function Tests (ALT/AST), fibrinogen, whole blood viscosity analysis, NMR lipoprotein subclass analysis, Apo B, lipoprotein (a), biocellular marker analysis, Oxidized lipid Analysis

Visit 4 (Week 4) ±7 days

- Review for AEs/SAEs/CV events
- Concomitant therapy
- Vital signs
- Dietary instruction; medication compliance reminder
- Seattle Angina Questionnaire 7 (SAQ7)
- SC IP administration, QM (in-clinic) and 30 minute post-injections observation

Visit 5 (Week 8) ±7 days

- Review for AEs/SAEs/CV events
- Concomitant therapy
- Vital signs
- Dietary instruction; medication compliance reminder
- Seattle Angina Questionnaire 7 (SAQ7)
- SC IP administration, QM (in-clinic) and 30 minute post-injections observation

Visit 6 (Week 12) ±7 days

- Body height, waist circumference
- Body weight
- Review for AEs/SAEs/CV events
- Concomitant therapy
- Dietary instruction; medication compliance reminder
- Seattle Angina Questionnaire 7 (SAQ7)
- Laboratory assessments: hematology (CBC), blood chemistry (creatinine/eGFR, electrolytes), Liver Function Tests (ALT/AST), fibrinogen, whole blood viscosity analysis, NMR lipoprotein subclass analysis, Apo B, lipoprotein (a), biocellular marker analysis, Oxidized lipid Analysis

Table 1. Schedule of Assessments

Schedule of Assessments	Screening	Baseline/ Randomization	Week 2	Week 4	Week 8	Week 12
Visit Number	1	2	3	4	5	6
Visit Window		± 7-28 Days	± 4 Days	± 7 Days	± 7 Days	± 7 Days
Informed consent	X					
Demographics & Medical history	X					
Vital signs (HR, BP)	X	X	X	X	X	X
ECG	X					
Review for AEs/SAEs/CV events		X	X	X	X	X
Concomitant therapy	X	X	X	X	X	X
Dietary instruction; medication compliance reminder	X	X	X	X	X	
Physical examination	X					
Body height, waist circumference	X					X
Body weight	X					X
Seattle Angina Questionnaire 7 (SAQ7)	X	X	X	X	X	X
Placebo Injection	X					
Laboratory Analyses:						
TSH	X					
Hematology (CBC)	X		X			X
Chemistry (creatinine/eGFR, electrolytes)	X		X			X
Liver Function Tests (AST, ALT)	X		X			X
Urine albumin to creatinine ratio (ACR)	X					X
HbA1c	X					
Local Lipid Panel	X					
Urine pregnancy (if applicable)	X					
Fibrinogen		X	X			X
lipoprotein(a), Apo B		X	X			X
Whole Blood Viscosity Analysis		X	X			X
NMR Lipoprotein Subclass Analysis		X	X			X
Biocellular Marker Analysis		X	X			X
Oxidized lipid Analysis		X	X			X
DNA/mRNA test		X				
Randomization		X				

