5.8 Laboratory Tests

5.8.1 Local Laboratory Tests

Local laboratory assessments include TSH, hematology, blood chemistry, liver function tests (LFTs), eGFR, HbA_{1c}, fibrinogen and urine ACR, Apo B, lipoprotein(a). Please see Table 1 for the exact schedule of all laboratory tests.

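### Section 3.1 sets an on-study HbA1c limit of 10%, but HbA1c is scheduled at screening only, so no scheduled assessment supplies the value needed to check it

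*Combined protocol and SAP*

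**What the plan says.** Section 3.1 gives the instruction and its qualification together. The instruction is "Subjects should continue on their stable dose of anti-hyperglycaemic therapies during the course of the study". The qualification is that "it is important that the haemoglobin A1c (HbA1c) does not rise above 10" per cent, and that severe hypoglycaemia, or frequent milder episodes, should not develop. The same section promises that "Safety assessments will be undertaken at each study visit", without naming HbA1c.

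The same threshold is used at entry: exclusion g) in Section 2.2 removes subjects with HbA1c above 10%.

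In Section 4, the Visit 1 laboratory list includes "HbA_{1c}, local lipid panel, urine albumin to creatinine ratio (ACR"). HbA1c is in no later list. The lists for Visit 3 (Week 2) and Visit 6 (Week 12) both begin "Laboratory assessments: hematology (CBC), blood chemistry (creatinine/eGFR, electrolytes), Liver Function Tests (ALT/AST), fibrinogen" and go on to viscosity, lipoprotein and biomarker tests. The Visit 2 list has neither HbA1c nor glucose. Visits 4 and 5 (Weeks 4 and 8) list no laboratory tests. Table 1 marks HbA1c once, under Screening. Section 5.8.1 names HbA1c as a local test and leaves its timing to the table: "Please see Table 1 for the exact schedule of all laboratory tests".

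**The concern.** The limit concerns what happens after entry, because it speaks of a rise and qualifies an instruction that runs for the whole study. The screening value serves eligibility and cannot show a later rise. Exclusion g) removes only values above 10%, so a subject at or just below 10% can enter with little or no margin and is then asked to hold therapy stable.

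If HbA1c rises past 10% in such a subject, nothing on the schedule would show it. At stake are the glycaemic safety of individual subjects and the sponsor's ability to show from study data that a limit it calls important was respected. The treatment comparison is not at stake.

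**Working it through.** The plan states no figure to reproduce. The check compares the limit with the schedule and then works out visit timing.

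**1. Count of scheduled HbA1c measurements** (Section 4 visit lists and Table 1)

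| Visit | HbA1c scheduled | Blood tests listed |
|---|---|---|
| 1 Screening | Yes | Yes |
| 2 Randomization | No | Yes |
| 3 Week 2 | No | Yes |
| 4 Week 4 | No | None |
| 5 Week 8 | No | None |
| 6 Week 12 | No | Yes |

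This gives 1 of 6 visits overall, 0 of 5 after screening, and 0 of 4 after the first dose. The visit lists and Table 1 agree on HbA1c, and other rows of the table keep their later marks, so the count does not depend on how the table was extracted.

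**2. Could another scheduled item stand in for it?**

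- Post-screening chemistry names creatinine/eGFR and electrolytes, with no glucose.
- Adverse event review at Visits 2 to 6 can pick up symptomatic hypoglycaemia, which covers the other part of the Section 3.1 qualification. It does not yield an HbA1c value.
- Section 6.1 has investigators assess changes in laboratory values, but a single screening value cannot show a change.
- The Section 3.1 promise of safety assessments at every visit is general, and Section 5.8.1 makes Table 1 the schedule for laboratory tests.

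**3. Age of the screening value at each possible check**

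Inputs from Section 4: screening precedes Day 1 by 7 to 28 days; the visit window is ±7 days at Weeks 4, 8 and 12.

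Formula: days from screening = (7 to 28) + 7 × study week. Weeks left = 12 − study week.

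| Visit | Nominal days since screening | Weeks | Days with window | Weeks left |
|---|---|---|---|---|
| Week 4 | 7+28=35 to 28+28=56 | 5–8 | 28–63 | 8 |
| Week 8 | 7+56=63 to 28+56=84 | 9–12 | 56–91 | 4 |
| Week 12 | 7+84=91 to 28+84=112 | 13–16 | 84–119 | 0 |

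A Week 12 value alone can record a breach but leaves no study time in which to act. A Week 4 or Week 8 value leaves 8 or 4 weeks.

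**4. Number of assays**

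The only subject count available is the completer target of 40 in Section 3.1. One added time point needs at least 1 × 40 = 40 assays, and two need at least 2 × 40 = 80. The number randomized is not stated and may exceed 40, so these are minimum figures.

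**The case against.** The strongest defence is that the Section 3.1 sentence is clinical guidance and not a monitoring requirement. HbA1c is a named local test, nothing bars an unscheduled or usual-care measurement, and Section 5.9 keeps the trial from driving medication changes, which is compatible with diabetes care staying with the treating physician. HbA1c above 10% is already excluded at entry and the treatment phase is only 12 weeks.

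Much of this stands. A reader might infer that a site following the protocol is unable to apply the limit at all. The documents do not support that, because an investigator may order the test or use a usual-care result. What remains is that no scheduled study assessment supplies the value, and the protocol nowhere assigns HbA1c monitoring to usual care. These points soften the gap without closing it.

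The defence could also hold that rewording Section 3.1 would be enough. That would remove the inconsistency on paper, but a breach would still be as likely to go unseen.

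**Conclusion.** The point holds as a minor safety-monitoring gap: a stated on-study limit, with 0 of 5 post-screening visits scheduled to measure it. A breach could go undetected at a site that follows the schedule exactly.

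Two further inferences should be resisted. The first is that the trial's results are affected. They are not: Section 3.5 contains no HbA1c withdrawal rule, no endpoint or analysis rule uses the limit, and the ANCOVA in Section 7.3 proceeds unchanged. The second is that a material number of subjects will pass 10%. The documents give no HbA1c distribution or expected drift, so that number cannot be estimated, and the intervals above describe visit spacing, not risk.

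The conclusion rests on reading the limit as applying after entry, which its wording supports, and on Table 1 and the visit lists being the complete laboratory schedule, as Section 5.8.1 indicates.

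**What to change.** - **During treatment:** add one HbA1c at Week 4 or Week 8. Both are in-clinic dosing visits ("SC IP administration, QM (in-clinic) and 30 minute post-injections observation"), so no visit is added. Week 4 leaves 8 weeks to act; Week 8 covers more of the interval but leaves 4. This is the measurement that lets the limit guide care.
- **At exit:** add HbA1c to the existing Week 12 draw, to document any breach and support referral when the subject leaves the study.
- **Text:** enter both in Table 1 and in the matching visit lists. State in Section 3.1 that a value above 10% leads to referral to the treating physician, with any resulting medication change recorded under Section 5.9. Making this a clinical-care referral keeps it consistent with that section.

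The cost is a short amendment, at least 40 assays per added time point (at least 80 for both), and one small extra blood sample per subject at Week 4 or Week 8, where none is now drawn. The Week 12 test needs no additional draw. The analysis plan does not change.
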